IVROP ReadyforLIFE Program Evaluation

Study Protocol

ClinicalTrials.gov ID: NCT05244447

August 29, 2024

Descriptive Evaluation Analysis Plan: "The Evaluation of ReadyforLIFE in Imperial Valley, California"

A. HMRE grant recipient

HMRE grant recipient: Imperial Valley Regional Occupation Program, El Centro, CA

Project lead: [name]

Email address: [contact]

B. Evaluator

Evaluator's organization: Midwest Evaluation and Research, Emporia, KS

Evaluator lead: [name]

Email address: [contact]

Descriptive Evaluation Analysis Plan

The Evaluation of ReadyforLIFE in Imperial Valley, CA

A. Description of the intended intervention(s)

The ReadyforLIFE program aims to support the development of healthy, respectful, nonviolent relationships among youth in the Imperial Valley region of California. The primary curriculum includes courses that provide all youth participants with a general overview of healthy partner and family relationships, healthy attitudes and habits about mental health, and money management. Primary workshops are offered predominantly as in-person, in-school sessions that occur during students' regular school hours, though in-person, after school and virtual, evening formats have also been offered to meet the needs of different students. Additionally, participants receive individualized Life Coaching sessions where they can explore career opportunities, get connected to other resources in the community, discuss future interests, and work with their Life Coach to develop an action plan for achieving future goals. A subset of program participants, selected based on their core programming participation and interest on a first-come first-served basis, subject to funding availability, are eligible to receive additional optional program services, described as 2.0 and PLUS services in the outline below. A summary of program services, including dosage and focal population, can be found in Table 1.

- **Goal 1 - Deliver core curriculum as primary services to all IVROP ReadyforLIFE participants:**
Participants receive *core curriculum* to develop healthy attitudes (relationship and financial) and skills to engage in healthy partner and family relationship behaviors, but only after receiving an orientation about the IVROP ReadyforLIFE Program and giving program staff informed consent to participate in study activities. Then, primary ReadyforLIFE curriculum is delivered. Primary curriculum, delivered by an IVROP facilitator, includes 12 hours of Relationship Smarts, 3 hours of Mind Matters, and 1 hour of Money Habitudes, for a total of 16 primary workshop hours, typically delivered sequentially over 4-5 weeks. For *in-person, in-school workshops*, the number of sessions and length of the workshop series varies depending on classroom schedules. In-school workshops are provided to students whose teachers have agreed to use classroom time to provide the ReadyforLIFE program to their students. ReadyforLIFE is typically offered as a replacement for instructional time in classes that focus on student health and life skills, such as Freshman Seminar, Success 101, or Intro to Health. For *in-person and virtual workshops* held after school, the delivery schedule is typically as follows:
 - **Relationship Smarts (12 hours total)** – three 2-hour sessions per week for two weeks
 - **Mind Matters (3 hours total)** – two 1.5-hour sessions held within one week, after the conclusion of Relationship Smarts
 - **Money Habitudes (1 hour total)** – one 1-hour session held either in the same week as Mind Matters or the following week, along with the exit session and makeup workshops as needed

Virtual and in-person afterschool workshops are typically attended by students who do not have teachers who are offering the program as part of the regular school day. Virtual, evening cohorts are typically made up of students who have extracurricular afterschool activities that prevent them from attending in-person, afterschool workshops.

- **Goal 2 - Deliver support services to all IVROP ReadyforLIFE participants:**

Program participants also receive *support services* in the form of individualized life coaching sessions by IVROP facilitators who have been trained in Life Coaching techniques. Life Coaches will offer sessions to build skills to promote independence, decision making, problem solving, and goal setting. Each program participant will be offered at least 3 sessions, to be held virtually or in person. In-person, in-school cohorts are offered Life Coaching services in person, often in a small group setting, and students are able to request 1-on-1 coaching sessions if they prefer. Life Coaching sessions can also be completed on the phone or via Zoom, depending on the needs and preferences of the student.

- **Goal 3 - Deliver ReadyforLIFE 2.0 Services (Primary + 2.0 services) to a select number of IVROP ReadyforLIFE primary curriculum completers:** Program participants, once they complete all primary services (i.e., 16 core curriculum hours), are eligible to receive ReadyforLIFE 2.0 services. Each grant year, 100 students will be offered 2.0 services on a first-come, first-served basis. ReadyforLIFE 2.0 services include the following program activities, with a delivery schedule that varies based on setting:
 - **Career Readiness course (6 hours total)**
 - In-person, in-school: 1 hour per day for 6 school days
 - Virtual or in-person after school: 2 hours per day for 3 days within 1 week
 - **Work-based learning activities with a partner agency (10 hours total)** to be completed within 2 weeks outside of school
 - One activity, up to 8 hours (employer-based mentoring OR job shadowing)
 - Employer-based mentoring (either individual or with a small group of participating students) includes discussions about how students can stay on the path toward a particular field (i.e., tips and insights), while job shadowing allows students the opportunity to observe a day in the life of an employee in a particular field
 - One 2-hour activity (employer presentation OR industry tour)
 - At least one **additional workshop (time varies based on selection – students choose based on their individual interests)**
 - Option 1: **Developmental Assets course using the Developmental Assets Framework curriculum developed by the Search Institute (4 hours total)**
 - In-person, in-school: 1 hour per day for 4 school days
 - Virtual or in-person after school: 2 hours per day for 2 days **OR**
 - Option 2: **First5 Parenting workshop using resources developed by First5 California (8 hours total)**
 - In-person, in-school: 1 hour per day for 8 school days
 - Virtual or in-person after school: 2 hours per day for 4 days
 - Participants who are interested in continuing through to ReadyforLIFE PLUS services (Goal 4) must complete both the Developmental Assets and First Five Parenting workshops, as well as the Career Readiness course and work-based learning activities.
- **Goal 4 – Delivery ReadyforLIFE PLUS Services (Primary, 2.0, and PLUS services) to a select number of ReadyforLIFE Primary and 2.0 curriculum completers:** Program participants, once they complete all Primary and 2.0 services (i.e., 16 hours of core curriculum and 28 hours of 2.0 programming), are eligible to receive ReadyforLIFE PLUS services. Each grant year, 35 students who meet these criteria will be offered ReadyforLIFE PLUS services on a first-come, first-served

basis. ReadyforLIFE PLUS services are offered in partnership with employers in the Imperial Valley. Employer partners are identified based on the interests of participating students; IVROP has employer partnerships in agriculture, retail, and health care, among other sectors, and students are able to choose which sectors interest them. ReadyforLIFE PLUS services include the following activities:

- **Work-based learning activities with a partner agency (20 hours total, inclusive of 10 hours completed as part of 2.0)** to be completed within 4 weeks outside of school
 - Participants will complete all of the work-based learning activities from 2.0 (employer-based mentoring, job shadowing, employer presentation, and industry tour) with a partner agency
- **Paid work experience with partner employers (up to 160 hours)**
 - During school year – maximum of 20 hours per week
 - During summer – 40 hours per week for 4 weeks

Table 1. Description of intended intervention components, content, dosage and implementation schedule, delivery, and focal populations

Components	Content	Dosage and schedule	Delivery	Focal population
Relationship skills workshops	Relationships Smarts Plus curriculum: skill-building for youth to have healthy relationships with committed partners	A total of 12 hours, with two-hour sessions occurring three times per week for two weeks (can vary by classroom schedule for in-person, in-school services)	Group classes provided either 1) in-person, in-school, 2) in-person, after school at IVROP facilities, or 3) virtually after school; two trained facilitators lead every session	At-risk youth (defined as attending a high-need high school or meeting other risk criteria such as membership in a low-income or single parent household) ages 14-18 and enrolled in 9-12th grades
Mental health workshops	Mind Matters curriculum: skill-building that helps youth resolve ACEs to manage emotions and improve their state of mind	A total of three hours, with two 1.5-hour sessions held within one week	Group classes provided either 1) in-person, in-school, 2) in-person, after school at IVROP facilities, or 3) virtually after school; two trained facilitators lead every session	At-risk youth (defined as attending a high-need high school or meeting other risk criteria such as membership in a low-income or single parent household) ages 14-18 and enrolled in 9-12th grades
Economic stability workshops	Money Habitudes curriculum: skill-building that uses personality types to develop better money attitudes and habits	A total of one hour, with one 1-hour session held in the same week as Mind Matters or the following week	Group classes provided either 1) in-person, in-school, 2) in-person, after school at IVROP facilities, or 3) virtually after school; two trained facilitators lead every session	At-risk youth (defined as attending a high-need high school or meeting other risk criteria such as membership in a low-income or single parent household) ages 14-18 and

Components	Content	Dosage and schedule	Delivery	Focal population
Life coaching sessions	Individualized sessions to promote independence, decision making, problem solving, and goal setting	At least three 1-hour sessions	Individual sessions provided by IVROP-trained Life Coaches either virtually or in person	enrolled in 9-12th grades At-risk youth (defined as attending a high-need high school or meeting other risk criteria such as membership in a low-income or single parent household) ages 14-18 and enrolled in 9-12th grades
ReadyforLIFE 2.0 (optional, secondary for up to 100 students per grant year)	Career readiness course; work-based learning activities; parenting or developmental assets course provided by IVROP facilitators	A total of 20-28 hours (depending on selections; course schedule can vary by classroom schedule for in-person, in-school services)	Group classes provided either 1) in-person, in-school, 2) in-person, after school at IVROP facilities, or 3) virtually after school; group work-based learning activities with partner employers or IVROP's Strong Workforce agency	At-risk youth (defined as attending a high-need high school or meeting other risk criteria such as membership in a low-income or single parent household) ages 14-18 and enrolled in 9-12th grades who complete all ReadyforLIFE primary services
ReadyforLIFE Plus (optional, secondary for up to 35 students per grant year)	Work-based learning activities; paid work experience	Up to 180 hours total, with a maximum of 20 hours per week of paid work experience during the school year and a maximum of 40 hours per week of paid work experience during the summer	Individual/group work-based learning activities and individual paid work with partner employers	At-risk youth (defined as attending a high-need high school or meeting other risk criteria such as membership in a low-income or single parent household) ages 14-18 and enrolled in 9-12th grades who complete all ReadyforLIFE primary and 2.0 services

Table 2. Staff education and training (initial and ongoing)

Component	Education and initial training	Ongoing training
Relationship skills workshops	Facilitators: 1 male and 4 females All facilitators hold a bachelor's degree and received 5 days (17.5 hours) of initial training.	Receive yearly refresher trainings during seasonal breaks to include, school's thanksgiving and summer breaks, and attend semiannual content webinars that cover curriculum enhancements offered by the Dibble Institute .

Component	Education and initial training	Ongoing training
Mental health workshops	Facilitators: 1 male and 4 females All facilitators hold a bachelor's degree and received 5 days (17.5 hours) of initial training.	Receive yearly refresher trainings during seasonal breaks to include, school's thanksgiving and summer breaks, and attend semiannual content webinars.
Economic stability workshops	Facilitators: 1 male and 4 females All facilitators hold a bachelor's degree and received 2 days (5 hours) of initial training.	Receive yearly refresher trainings during seasonal breaks to include, school's thanksgiving and summer breaks, and attend semiannual content webinars.
Life coaching sessions	Facilitators: 1 male and 4 females All facilitators hold a bachelor's degree and received 30 contact hours of Life Coach training for certification, in addition to completing 20 practicum hours.	Receive yearly refresher trainings during seasonal breaks to include, school's thanksgiving and summer breaks, and attend semiannual content webinars.
Career readiness workshops	Facilitators: 1 male and 4 females All facilitators hold a bachelor's degree and received 3 days (6 hours) of initial training.	Receive yearly refresher trainings during seasonal breaks to include, school's thanksgiving and summer breaks, and attend semiannual content webinars.
Developmental Assets workshops (for 2.0 participants only)	Facilitators: 1 male and 4 females All facilitators hold a bachelor's degree and received an initial curriculum training	Receive yearly refresher trainings from Search Institute during seasonal breaks to include schools' Thanksgiving and summer breaks
First5 Parenting workshops (for 2.0 participants only)	Facilitators: 1 male and 4 females All facilitators hold a bachelor's degree and received an initial training with First5 California	IVROP staff who received the initial training from First5 conduct train-the-trainer refreshers among staff

B. Outcomes study

This section describes the research questions, evaluation enrollment process, data collection procedures, outcome measures, and analytic approach for the outcomes study.

1. Research questions

RQ1: What is the level of healthy relationship attitude scores immediately following ReadyforLIFE primary services, as compared to baseline scores?

RQ2: What is the level of healthy relationship behavior scores one year after enrollment into ReadyforLIFE primary services, as compared to baseline scores?

RQ3: What is the level of healthy financial attitude scores immediately following ReadyforLIFE primary services, as compared to baseline scores?

RQ4: What is the level of healthy financial behavior scores one year after enrollment into ReadyforLIFE primary services, as compared to baseline scores?

2. Outcomes evaluation enrollment

The original study and data collection plan were initially approved by Solutions IRB on 3/30/2021 and have been annually reviewed and approved three times on 3/15/2022, 3/4/2023, and 3/11/2024.

Additionally, revisions to the study and/or data collection plan were submitted to the IRB as amendments and were approved on 4/6/2022 and 2/22/2023.

All program participants whose parents have given consent are eligible to participate in the evaluation study. Participants for the ReadyforLIFE program, and thus the study, are recruited primarily from partnerships with schools and particular teachers in the Imperial Valley region who have agreed to offer ReadyforLIFE programming as part of their classroom instructional time. IVROP staff give presentations to school administrators and directly to students to foster interest in the program. Monthly presentations directly to students in classrooms generate an interest list that IVROP uses to fill after school and summer workshops. Program service locations participating in the local evaluation since the start of the program have included:

- Brawley Union High School
- Central Union High School
- Calipatria High School
- Southwest High School
- Holbrook High School
- Desert Valley High School
- Renaissance High School
- Phoenix Rising High School
- After-school services provided at IVROP facilities
- Virtual services provided via Zoom

The projected enrollment into the study is 1680 participants, and the desired sample size, with a target follow-up survey response rate of 70%, is 1176 participants.

To be eligible for the program, and thus the study, participants must meet the following criteria: 1) at-risk youth (e.g., former foster care system involved, runaways, homeless, low income, migrant, at risk for dropping out of school, expecting or parenting teens, or attending a Title 1 or alternative high school), 2) ages 14-18, 3) parents have given consent for youth to participate, and 4) youth have given assent to participate in the study. All students offered services in a classroom setting meet the first criterion, as services are offered in Title 1 or alternative high schools. Enrolling students are also asked to identify if they meet other risk criteria (e.g., low-income household, single parent household, etc.). Eligibility for virtual and after school workshops is determined by the IVROP program manager using responses on the enrollment packet paperwork.

Parental consent for enrollment into the evaluation is collected as part of the program enrollment process. A consent form explaining study activities and potential risks and benefits is provided to parents as part of the enrollment packet with information on who to contact with questions. Parents who wish to

deny consent for their youth to be part of the study will sign and return the form to program staff. Youth assent for enrollment into the evaluation happens during program orientation, prior to the start of the first primary workshop. The study activities and potential risks and benefits are explained to the youth, who have an opportunity to opt out of the local evaluation. Consent records are kept on MER's secure Dropbox server.

Enrollment into the study began on June 15, 2021 and is expected to continue until March 31, 2024, after which point study enrollment will end to allow for collection of the one-year follow-up survey before final analyses and report writing begin in 2025.

3. Data sources and data collection

The main data source for this study is surveys of intervention participants. Participants are surveyed at three different time points throughout the study. Two surveys (one nFORM and one local evaluation [OLLE] survey) are collected from participants at each of the first two waves of data collection. Wave 1 (nFORM entrance survey and OLLE pre-survey) of data collection happens during the program orientation session before the first primary workshop session, with make-ups administered as needed until three primary workshops have been received. Wave 2 (nFORM exit survey and OLLE post-survey) of data collection happens at or immediately after the final workshop session, with make-ups administered as needed for up to two weeks after primary workshops end. Wave 3 of data collection (the OLLE follow-up survey) happens one year after program enrollment.

Waves 1 and 2 of surveys are administered online using students' school computers, program tablets, or students' personal devices in the case of virtual cohorts. Paper surveys can be offered if necessary due to technological difficulties or facility restrictions. The link to complete the follow-up survey at Wave 3 is sent to participants via email, text message, and postcard/letter using a QR code. Participants can also complete the survey over the phone with evaluation team staff if they prefer.

Wave 1 of data collection began in June 2021 and will conclude at the end of March 2024. Wave 2 of data collection began in July 2021 and is expected to conclude in April 2024. Wave 3 of data collection began in June 2022 and is expected to conclude in March-April 2025.

The analyses for this study will use data from different survey waves, depending on the outcome. Short-term attitudinal changes will be assessed by comparing outcomes between Waves 1 and 2 (program entry to exit), and longer-term behavioral changes will be assessed by comparing outcomes between Waves 1 and 3 (program entry to follow-up).

A copy of the local evaluation survey codebook will be sent as a separate appendix to this plan.

Table 3. Sources of data to address the research questions

Data source	Timing of data collection	Mode of data collection	Start and end date of data collection
Intervention participants (nFORM entrance survey and OLLE pre-survey)	At the orientation session before the first primary workshop	In-person online survey or remote online survey	June 2021-March 2024

Data source	Timing of data collection	Mode of data collection	Start and end date of data collection
Intervention participants (nFORM exit and OLLE post-survey)	At or immediately after the final primary workshop session with make-ups offered as needed	In-person online survey or remote online survey	August 2021-May 2024
Intervention participants (OLLE follow-up survey)	One year after program enrollment	Remote online survey sent via text, email, or QR code; phone survey	June 2022-March 2025

4. Outcome measures

The attitudinal research questions for this study will be answered by comparing post-survey responses collected at the end of primary workshop services to baseline survey responses collected before primary workshops begin. The behavioral research questions for this study will be answered by comparing follow-up survey responses collected one year after program enrollment to baseline survey responses collected before primary workshops begin. The one-year follow-up survey will be administered to all program participants who consent to be in the study and complete at least one baseline survey (nFORM or OLLE), regardless of program completion status or workshop delivery format. Because the post-surveys (nFORM exit and OLLE post-survey) are collected during or shortly after the final primary workshop, it is likely that only those complete the program will complete the post-surveys; however, all study participants who have consented and completed at least one baseline survey are eligible to take the post-surveys.

For each outcome construct (healthy relationship attitudes, healthy relationship behaviors, healthy financial attitudes, and healthy financial behaviors), we have identified the relevant survey measures that are theoretically aligned with that construct. When analysis begins, we will generate a correlation matrix between items in a given construct to ensure that theoretically related items are also empirically related in our data set. Survey items will be reverse-coded as needed before checking for correlation strength. Items that are not strongly correlated with other items in a construct will be removed as necessary. Factor analysis will be used to ensure that all construct items hang together, using an alpha of 0.7 or higher as the acceptable threshold. If a constructed scale does not achieve an alpha of 0.7 or higher, even after removing items that are not well correlated, the outcome measure will be dropped from the analysis.

We will then create a composite measure for each construct by taking an average of the scores on each non-missing item in the construct. For these composite measures, we intend to use 20% as a threshold for allowable missing items; this plan is contingent on the final distribution of missing data in our data set. Participants who are missing more than 20% of items for a given construct will be assigned a missing value for that composite outcome measure. We will not be imputing truly missing values for outcomes. To create the construct score for each participant, the average of the relevant survey items will be divided by the number of non-missing values in the construct.

Table 4. Outcomes used to answer the research questions

Research question	Outcome name	Description of the outcome measure	Source of the measure	Timing of measure
RQ1	Healthy relationship attitudes	The outcome measure is a scale (value range 1-4) calculated as the average of nine survey items related to healthy relationship beliefs	nFORM entrance survey (A1.a-i); nFORM exit survey	Wave 1 (before primary workshops begin) and Wave 2 (at the final primary workshop)
RQ1	Healthy relationship attitudes	The outcome measure is a scale (value range 1-5) calculated as the average of three survey items related to expectations that youth have for their future relationship circumstances	nFORM entrance survey (A2.a-c); nFORM exit survey	Wave 1 (before primary workshops begin) and Wave 2 (at the final primary workshop)
RQ2	Healthy relationship behaviors	The outcome measure is a scale (value range 1-4) calculated as the average of five survey items related to reported self-assessed skill with communication and conflict resolution	nFORM entrance survey (C1b.a-e); OLLE follow-up survey	Wave 1 (before primary workshops begin) and Wave 3 (one year after program enrollment)
RQ2	Healthy relationship behaviors	The outcome measure is a scale (value range 1-5) calculated as the average of six survey items related to the frequency of engaging in unhealthy conflict resolution behaviors	nFORM entrance survey (C3.a-f); OLLE follow-up survey	Wave 1 (before primary workshops begin) and Wave 3 (one year after program enrollment)
RQ3	Healthy financial attitudes	The outcome measure is a scale (value range 1-5) calculated as the average of seven survey items related to level of agreement with key financial attitudes	OLLE pre-survey (Q14.a-g); OLLE post-survey	Wave 1 (before primary workshops begin) and Wave 2 (at the final primary workshop)
RQ4	Healthy financial behaviors	The outcome measure is a scale (value range 1-5) calculated as the average of four survey items related to level of agreement with good money management habits	OLLE pre-survey (Q21.a-d); OLLE follow-up survey	Wave 1 (before primary workshops begin) and Wave 3 (one year after program enrollment)

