IVROP ReadyforLIFE Program Evaluation

Statistical Analysis Plan

August 29, 2024

ClinicalTrials.gov ID: NCT05244447

Analysis approach

The main goal of this descriptive study is to assess pre-post change scores in the means of the outcome constructs listed above among program participants before, immediately following, and one year after primary workshops. We will use paired sample t-tests to assess the magnitude and significance of mean score changes among program participants in the analytic sample for each outcome.

The analytic sample for each outcome construct consists of study participants who have a non-missing value at baseline and follow-up time points for that outcome (complete case). The analytic sample may vary by outcome construct based on prevalence of missing data at the baseline, post, or follow-up surveys for those questions. The final report will include descriptive statistics about the sample for each outcome, including which optional services (2.0, PLUS, or none) that participants received. As mentioned in the Outcomes section above, a respondent who answers some but not all survey items in a given outcome construct matrix will have their outcome value assigned as missing if they do not respond to at least 80% of the items in the construct. We will not impute missing baseline or outcome data for our analyses. Findings are considered statistically significant based on $p < 0.05$, two-tailed test. We will adjust our p-values for multiple hypothesis testing and report the adjusted p-values in the appendix of the final report.

As part of data preparation and cleaning, we will check for inconsistent and seemingly inaccurate data. The largest source of potentially inconsistent data that we anticipate is duplicate local evaluation surveys. Participants are able to, and occasionally do, retake the local evaluation surveys on Qualtrics. In the case of duplicate survey data, where participants have taken a local evaluation survey more than one time, we plan to take the following approach:

- Check for incorrectly entered Client IDs that inaccurately flag surveys as duplicates. Using the name and/or DOB fields on the local evaluation survey, we will check that responses that appear to be duplicates were in fact collected from the same participant multiple times (i.e., are true duplicates). If not, we will correct Client IDs as necessary.

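### The 20% missing-item rule allows no skipped item on RQ4's only scale (four items) or on the three-item expectations scale, and its threshold may still change once missing data are seen

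*Protocol*

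**What the plan says.** Protocol section B.4 (Outcome measures) builds each outcome as the mean of the answered items, subject to a limit: "Participants who are missing more than 20% of items for a given construct will be assigned a missing value for that composite outcome measure". The SAP (Analysis approach) gives the same limit from the other side: a partial responder "will have their outcome value assigned as missing if they do not respond to at least 80% of the items in the construct".

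Table 4 of the Protocol applies this to six scales of different lengths. The shortest two are an RQ1 scale "calculated as the average of three survey items related to expectations that youth have for their future relationship circumstances" and the sole RQ4 scale, "calculated as the average of four survey items related to level of agreement with good money management habits". The others have nine items (RQ1), five and six (RQ2) and seven (RQ3).

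Three other provisions matter:

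- The SAP restricts each analysis to youth with a score at both time points and imputes nothing.
- Section B.4 lets the scales shrink before scoring: "Items that are not strongly correlated with other items in a construct will be removed as necessary".
- Section B.4 qualifies the 20% figure: "this plan is contingent on the final distribution of missing data in our data set". The SAP states the 80% rule without that qualification.

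**The concern.** A fixed percentage behaves differently on scales of three to nine items. The plan presents the rule as a tolerance for missing items, but on two of its six scales the tolerance is zero, and neither document says so. RQ4 is the most exposed because it has no second scale. A youth who gave seven of the eight RQ4 answers across Waves 1 and 3 would be excluded from that research question, whereas one skip on the seven-item RQ3 scale costs nothing. Precision would fall, and the RQ4 sample would be restricted to youth who answered every item twice.

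The rule also interacts with item pruning. The five-item RQ2 skill scale sits exactly on the 20% boundary, so whether a youth with one skip is scored can depend on a correlation check made on the same data. Finally, an inclusion threshold that may be revised after missingness is examined, with no criterion for revising it, is not pre-specified.

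**Working it through.** **The plan's own figure.** Section B.2 of the Protocol projects 1680 enrolled and a 70% follow-up response: 1680 × 0.70 = 1176, as stated. No power calculation is given.

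**Skips allowed.** For a scale of k items, the limit is the largest j with j/k ≤ 1/5. The SAP form, (k − j)/k ≥ 4/5, gives the same answer.

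| Scale (Table 4) | Items | One skip | Skips allowed |
|---|---|---|---|
| RQ1 expectations | 3 | 33.3% | 0 |
| RQ4 money management | 4 | 25.0% | 0 |
| RQ2 self-assessed skill | 5 | 20.0% | 1 |
| RQ2 conflict behaviors | 6 | 16.7% | 1 |
| RQ3 financial attitudes | 7 | 14.3% | 1 |
| RQ1 beliefs | 9 | 11.1% | 1 |

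The five-item scale passes only because 20% is not more than 20%. Pruned to four items, it allows none. The six-item scale pruned to five keeps its one.

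**RQ4 pairs.** The scale must be complete at both waves: 4 + 4 = 8 answers.

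**Illustrative size.** The documents give no item-skip rate, so q, the chance that a survey responder skips an item, is an assumption; skips are first taken as independent.

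- Rule as written: usable share = (1 − q)^8.
- One skip allowed per wave: usable share = [(1 − q)^4 + 4q(1 − q)^3]².

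For example, at q = 0.02 the first is 0.98^8 = 0.8508. The second is (0.9224 + 0.0753)² = 0.9953.

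| q | As written | Of 1176 | One skip allowed | Of 1176 |
|---|---|---|---|---|
| 1% | 92.3% | 1085 | 99.9% | 1175 |
| 2% | 85.1% | 1000 | 99.5% | 1171 |
| 3% | 78.4% | 922 | 99.0% | 1164 |
| 5% | 66.3% | 780 | 97.2% | 1143 |

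The loss is therefore 8% to 34% as written, and about 0.1% to 3% with one skip allowed.

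**Clustered skips.** Skipping may concentrate in some youth. With a beta-binomial in which each youth's tendency to skip is shared across both waves (assumed intra-youth correlation 0.3), the counts at the same four rates are 1131, 1087, 1045 and 965 as written, against 1159, 1142, 1125 and 1089 with one skip allowed. The difference is 28, 55, 80 and 124 youth, or 2.4% to 10.5% of 1176.

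**What 1176 stands for.** It is the number of follow-up responders at the 70% target, not a count of RQ4 pairs. Section B.4 admits youth with only one of the two baseline surveys, so some responders may lack the OLLE pre-survey that RQ4 needs. At that response rate, 1176 is an upper reference. The SAP (Attrition) reports follow-up response currently over 80%; the percentages above do not depend on this.

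**The case against.** Requiring complete answers on a three- or four-item scale is a defensible choice, and the two documents state the limit consistently. It also avoids a bias: averaging the answered items assumes that they have similar means. If four items had means of 3, 3, 3 and 4 (assumed) and the last were skipped at one wave only, the score would move from 3.25 to 3.00, an artificial change of 0.25. On three items with means 3, 3 and 4 the shift is 0.33. This stands as a cost of any relaxation, and it is why scoring two of three items belongs in a sensitivity check.

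The size is assumed, and independent skipping is unfavorable to the rule. If youth skip a whole block of questions, allowing one skip rescues nobody. The effect on precision is also modest at low rates: relative to allowing one skip, the standard error rises by √(1175/1085) = 1.04 at 1%, √(1171/1000) = 1.08 at 2%, and √(1143/780) = 1.21 at 5%. All of this stands. It limits how strongly the point can be put but does not change the arithmetic.

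The SAP's Attrition section will report, by outcome, how many youth are lost to the threshold and will compare youth in and out of the sample on baseline responses, gender and age. That makes the loss visible but does not prevent it. The contingency clause might be read as the remedy, but it gives no criterion and would operate after the data are seen.

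If RQ1's two scales were pooled as one construct of 12 items, two skips would be allowed. Table 4, however, lists them as separate scales with ranges 1–4 and 1–5, so the per-scale reading is the natural one. RQ4 is unaffected.

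A reader might infer that analytic samples differ between outcomes only because of scale length. The documents do not support that: the scales come from different surveys (nFORM or OLLE) and different waves, and section B.4 expects Wave 2 to be answered mainly by program completers. Nor do they show that a large share of RQ4 will be lost, or that youth who skip items differ from those who do not.

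**Conclusion.** The point holds as a matter of arithmetic. The rule allows no skip on the three- and four-item scales and one on each of the others, and RQ4 requires all eight answers. The pruning effect is real but conditional: an item must be dropped from the five-item scale, and the youth must have skipped one that remains. Conversely, a youth whose only skip is a pruned item is regained.

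How many RQ4 pairs this costs cannot be determined from the documents; the ranges above are only as good as the assumed skip rates and the assumed independence or clustering. This is a worthwhile, inexpensive improvement to a descriptive study rather than an error that invalidates it. Fixing the threshold in advance is justified whatever the skip rate proves to be.

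**What to change.** In Protocol section B.4 and the SAP's Analysis approach, replace the 20%/80% rule with: *A scale score is the mean of answered items when at most one item is missing and at least three items are answered, applied after any item removal.*

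- The five-, six-, seven- and nine-item scales, as listed, are scored exactly as now.
- The four-item RQ4 scale gains a one-skip tolerance, and the five-item RQ2 scale keeps its own if pruned to four.
- The three-item scale still needs all its answers. The floor of three stops a scale pruned to two items from being scored on a single answer; it also means that such a scale would have no score at all, which the text should say.

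Delete the clause "this plan is contingent on the final distribution of missing data in our data set" so that the threshold is settled before the data are examined. Update the SAP's Attrition section, which names the 20% threshold as a reason for missingness.

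Report two sensitivity checks: RQ4 with all items answered, and the expectations scale scored on two of three items.

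The cost is one sentence in each document, a one-line scoring change and two extra analyses. The downside is that scores from three of four items are slightly noisier and can shift slightly if item means differ; the RQ4 check would show whether that matters.
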